We hypothesize that SGLT2 inhibition acutely reduces the kidneys demand for oxygen by reducing renal metabolism due to blocked sodium-glucose transportation, and hyperfiltration. We hypothesize that the following changes can be demonstrated after institution of SGLT2 inhibition:

- 1) Lowering of renal artery flow (PC-MRI)
- 2) Lowering of renal cortical perfusion and the ratio of cortical/medullary perfusion (ASL-MRI)
- 3) Better medullary oxygenation: Lowering of the renal medulla T_2^* (BOLD-MRI)
- 4) Decrease of renal oxygen consumption (Q-flow combined with measurement of BOLD in renal artery and vein)

We further hypothesize that autonomic function will improve, and that peripheral blood oxygenation and mitochondrial function will both increase after institution of SGLT2 inhibition.

Study population

Fifteen healthy controls recruited through an advertisement in the local newspapers and 15 persons with type 1 diabetes recruited from Steno Diabetes Center Copenhagen according to the study in-and exclusion criteria.

Inclusion criteria healthy controls:

- Written informed consent must be provided before participation
- Male or female patients > 18 years of age
- Capable of lying in a MR-scanner for two hours

Inclusion criteria persons with type 1 diabetes:

- Written informed consent must be provided before participation
- Male or female patients >18 years of age with a diagnosis of type 1 diabetes (WHO criteria)
- Urinary albumin creatinine ratio (UACR) ≥ 30 mg/g in 2 out of 3 consecutive samples (albuminuria) prior to randomization assessed from electronic laboratory database.
- Capable of lying in a MR-scanner for two hours

Exclusion criteria for all:

- Non-diabetic kidney disease as indicated by medical history and/or laboratory findings
- Renal failure (eGFR<15 ml/min/1.73m²), dialysis or kidney transplantation
- Treatment with beta-blocking medication
- Uncontrolled arrhythmia, 2. or 3. degree AV-block or sick sinus syndrome - assessed from a standard 12-lead electrocardiogram
- Pregnancy or breastfeeding (urine HCG is performed on all fertile women)
- Systolic blood pressure < 90 or > 200 mmHg
- Patients who, in the judgement of the investigator, is incapable of participating
- Exclusion criteria for MRI
 - Claustrophobia
 - Known heart disease

- Known lung disease
- Have had surgery the past six weeks
- Have foreign bodies of metal in the body (e.g. pacemaker, metal plates, metal screws)

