Information about civil registration number, phone number, address, diagnosis of T1D and historic levels of urine albumin on outpatients at Steno Diabetes Center Copenhagen is provided by the treatment-responsible doctor and passed on to the study investigator. This information is used for identifying possible participants and recruitment. First contact will be a letter containing the written participant information and the brochure: "Your rights as a participant in biomedical research". In the letter, possible participants will be invited to the information meeting at Steno Diabetes Center Copenhagen. The letter contains telephone number and email for the project-responsible doctor. Non-responders will be followed up by a telephone contact approximately two weeks later. All who wish to participate in the study are invited for an information visit.

Healthy controls will be recruited by advertisement in the local newspapers. In the advertisement, there will be phone number and email of the investigators for contact.

Endpoints

Primary end-point

- Renal oxygenation (T_2^*)

Exploratory end-points

[figure not shown]
- Renal cortical and medullary perfusion
- Renal artery flow
- Renal oxygen consumption
- Peripheral capillary oxygen saturation (SpO_2)
- Arterial blood gasses
 - Arterial blood oxygen partial pressure (PaO_2)

- Arterial blood oxygen saturation (SaO₂)
- PBMC mitochondrial function
- Circulating inflammatory markers
- Baroreflex sensitivity

Study design

Randomized, double blinded, placebo-controlled, cross-over intervention study in patients with type 1 diabetes. Baseline results will be compared to healthy controls.

Figure 1

Flowchart of study design. Healthy controls (CON) will only come for baseline measurements on V1 and V2, except blood gas analysis, which will only be done in randomized patients.

Patients with type 1 diabetes (T1D) will be randomized to SGLT2i or placebo for Visits 1+2 and crossed over for Visits 3+4.

Comparative treatment regimes

Patients in the active arm will be treated with dapagliflozin 50 mg once on site for V2 and once at home on the evening before V3.

Randomization and blinding

Patients will be randomly assigned in a 1:1 ratio to one of the following groups:

- Dapagliflozin for V2 and V3 and placebo for V4 and V5
- Placebo for V2 and V3 and dapagliflozin for V4 and V5

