Information about the study background, design and aspects of the study will be given by the investigator. After consideration, the participants interested in participating in the study are asked to sign an informed consent form. After signed informed consent, patients will be randomized. See section "Participant information/informed consent" for details on informed consent.

Visit 1 (day 7±6) at Steno Diabetes Center Copenhagen

The study participant will come fasting from the morning and abstinent from medication, alcohol and tobacco use except long-acting insulin, 24 hours before the visit. The study participant is not allowed to do strenuous exercise 24 hours prior to the examination. Visit 1 will take approximately two hours. The following questions, measures and samples are obtained:

- Demographic information, medication and medical history are obtained from electronic medical journal and by interview with the study participant
- Weight and height for calculation of body mass index (BMI)
- Office blood pressure and heart rate
- Routine biochemistry
- Test battery A (baseline)
 - Analysis of mitochondrial function of peripheral blood monocytes
 - Sample kept in research biobank for analysis of inflammatory markers
 - Baroreflex sensitivity assessed by continuous ECG and blood pressure

Visit 2 (day 14±6) at Rigshospitalet Glostrup

The study participant will come fasting from the morning and abstinent from medication, alcohol and tobacco use except long-acting insulin, 24 hours before the visit. The study

participant is not allowed to do strenuous exercise 24 hours prior to the examination. Visit 2 will take approximately eight hours. The following measures will be obtained:

- Test battery B (baseline)
 - MRI session with two measurements of: Renal perfusion, renal artery flow, renal oxygen consumption and T_2^* respectively
 - Peripheral blood oxygen saturation by pulse oximetry
 - Blood gas analysis

A standardized morning meal will be given together with the intervention: Institution of 50 mg SGLT2i/placebo. Exactly three hours after intervention, test battery B will be repeated:

- Test battery B (+3 hours)
 - MRI session with two measurements of: Renal perfusion, renal artery flow, renal oxygen consumption and T_2^* respectively
 - Peripheral blood oxygen saturation by pulse oximetry
 - Blood gas analysis

Then a standardized lunch will be given. Exactly six hours after intervention, test battery B will be repeated:

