Mitochondrial function		x		x		x
Inflammatory markers		x		x		x
Baroreflex sensitivity		x		x		x
Kidney MRI			x		x	
Pulse oximetry			x		x	
Blood gas analysis			x		x	
Safety						
Adverse events			x	x	x	x
Study medication						
Drug accountability				x		x

Study timetable for randomized patients. SDCC = Steno Diabetes Center Copenhagen, RHG = Rigshospitalet Glostrup.

Assessment of efficacy

In order to assess the acute physiological response of inhibiting SGLT2 in the proximal tubule, kidney MRI parameters, pulse oximetry and blood gas analysis are obtained before intervention (baseline), three hours after intervention and six hours after intervention. In order to assess the subacute, systemic physiological response, PBMC mitochondrial function, inflammatory markers and baroreflex sensitivity are obtained before intervention (baseline) and 12 hours after intervention. Baseline levels will be compared to those of healthy controls.

Response to dapagliflozin in outcomes in randomized patients will be compared to response to placebo.

Assessment of safety

Definition of SAE, SAR and SUSAR

Serious Adverse Event (SAE):

A Serious Adverse event is an experience that treatment results in any of the following:

- Results in death
- Is life threatening (note: the term life-threatening refers to an event in which the patient was at risk of death at the time of the event; it does not refer to an event which hypothetically might have caused death if it was more severe)
- Requires inpatient hospitalization or results in prolongation of existing hospitalization
- Results in persistent or significant disability/incapacity
- Is a congenital anomaly/birth defect, or
- Is an important medical event that may not result in death, be life-threatening, or require hospitalisation may be considered a serious adverse event when, based upon appropriate medical judgement, they may jeopardise the patient or subject and may require medical or surgical intervention to prevent one of the outcomes listed in this definition.
- Suspicion of transmission of infectious agents must always be considered an SAE.

Serious Adverse Reaction (SAR):

A SAE for which a causal relationship to the study medication is at least possible i.e. a causal relationship is conceivable and cannot be dismissed.

Suspected Unexpected Serious Adverse Reaction (SUSAR):

A SAE which is unexpected and regarded as possibly or probably related to the study medication by the Investigator.

Reporting of SAE SAR and SUSAR

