All events meeting the definition of an AE must be collected and reported. This includes events from the first study-related activity after the subject has signed the informed consent until the end of the study. When reporting Adverse Events the following parameters must be recorded: study name, patient identification (subject number, initials, sex, age), event (preferably a diagnosis), IMP, reporter identification (name or initials), causality, outcome. Timelines for reporting of AE's is described in study timetable.

Assessment of adverse event

The following three definitions are used when assessing the severity of an AE: Mild (no or transient symptoms, no interference with the subject's daily activities), Moderate (marked symptoms, moderate interference with the subject's daily activities) and Severe (considerable interference with the subject's daily activities; unacceptable).

The following terms are used when assessing the causality between an AE and the IMP: Probable (good reason and sufficient documentation to assume a causal relationship), Possible (a causal relationship is conceivable and cannot be dismissed) and Unlikely (the event is most likely to ethology other than the IMP (Forxiga®).

Reporting at the end of the study

A final report on the AEs and SAEs is sent to the Danish Medicines Agency, the Regional Scientific Ethics Committee and to AstraZeneca within 12 months after the last patient has completed the project.

Statistical considerations

Sample size

The primary goal is to test the hypothesis that SGLT2 inhibition will improve renal oxygenation with a lowering of medullary T_2^* , as a marker of increased oxygenation. A power calculation was performed, based on data available from the study by Haddock. et al. (15). The mean \pm SD resting medullary T_2^* was 23 ± 4 . Assuming that SGLT2 inhibition will improve oxygenation 20%, the sample size required to demonstrate a significant effect with a power of 80% and a type 1 error of 5%, is 13 subjects per group. To account for technical difficulties, we included 15 in each group. Power calculation was performed using the power statement implemented in the SAS enterprise software 7.1 (SAS Institute, Cary, NC, USA).

Analysis

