All characteristics will be presented as means with standard deviation (SD) or if skewed distributions, as medians with interquartile range (IQR). For baseline characteristics, chi-squared test and Fischer's exact test will be used when appropriate. For testing group differences, unpaired student's t-test will be used. For testing the effect of the intervention, linear regressions analyses will be performed adjusting for baseline values of outcome variables. To fulfil the requirement of a normal distribution of the model residuals, determinants will be log-transformed where appropriate. Statistical significance is inferred as a two-tailed P-value < 0.05 . All analyses will be performed in SAS enterprise 7.1.

Data management

Source data identification and source data verification

All clinical study information in this study will be recorded, handled, and stored in a way that allows it accurate reporting, interpretation and verification.

Sponsor/investigator will provide direct access to source data/documents for study related monitoring, audit, IEC/IRB review, and regulatory inspection. Sponsor has made an agreement with the GCP-unit at the University of Copenhagen, Denmark, who will be monitoring the study in accordance with the ICH guidelines for GCP.

Subject data protection

There will be a transfer of information from the doctor responsible for the person in the clinic to the doctor responsible for the research of relevance to study participation and safety in the personal record. All information on study subjects is protected according to law on processing of personal data and the law of health. None of the study related blood samples or data will be stored or analyzed in countries outside the EU.

Data handling

Before initiating the study acceptance from the Danish Data Protection Agency will be obtained. A separate case report form (CRF) will be prepared for each study participant. All health-related matters and sensitive personal data will be handled in accordance with the Danish "act on Processing of Personal Data".

All health-related matters and sensitive personal data (CRF, blood test result etc.) will be depersonalized. All participants will be given a study number referring to their personal information, which will be stored securely and separately. Adequate blinding of all personal data during data processing and publication will be ensured.

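### Renal artery flow and renal oxygen consumption are compared between patients and unmatched controls with no allowance for body size, so a systematic size difference could read as a disease effect.

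*Combined protocol and SAP*

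**What the plan says.** The randomized crossover takes place in the patients with type 1 diabetes. The 15 healthy controls attend for baseline measurements only, and Assessment of efficacy gives their purpose: "Baseline levels will be compared to those of healthy controls". Table 1 shows that controls have the baseline kidney MRI at Visit 2. For patients, that session covers perfusion, renal artery flow, oxygen consumption and T2*. Renal artery flow and "Renal oxygen consumption" are listed under Exploratory end-points.

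The Background and Methods describe flow as measured in the renal artery by phase-contrast MRI. Oxygen consumption is obtained by combining vessel flow with BOLD readings in the renal artery and vein. No unit is given for either quantity, and no divisor such as BSA or kidney volume.

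The Analysis section says: "For testing group differences, unpaired student's t-test will be used". Its only adjustment, for baseline values of the outcome, belongs to the test of the intervention.

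Controls come from newspaper advertisements. Both groups admit men and women over 18, and no matching is described. Body size is recorded at Visit 1, but with one stated purpose: "Weight and height for calculation of body mass index (BMI"). A body-size unit appears in the eGFR exclusion criterion: "Renal failure (eGFR<15 ml/min/1.73m²), dialysis or kidney transplantation".

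**The concern.** T2* and ASL tissue perfusion describe local tissue and are not whole-kidney amounts. Flow through the renal artery is a total, and so is a consumption figure built from that flow. Such totals are expected to be larger in larger people, whatever the state of the kidney.

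An unpaired t-test on the raw totals therefore compares kidney physiology and body size together. Suppose the patients and the advertisement-recruited controls differ systematically in size, for example through a different sex mix. A difference in mean flow or oxygen consumption could then be reported as a feature of diabetes when some or all of it is size. BMI, the only planned use of weight and height, does not solve this: a short and a tall person can share a BMI and differ in BSA.

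The contrast is with healthy controls, which is the only use the plan makes of that group. The Background also notes that renal blood flow has been called mandatory for interpreting T2*, so a distorted flow contrast could colour how the patient-control T2* comparison is read.

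**Working it through.** **The plan's own figure.** The only sample-size calculation is for medullary T2*. Its inputs are that "resting medullary T_2^* was 23" with SD 4, a 20% change (0.20 × 23 = 4.6), and "with a power of 80% and a type 1 error of 5%, is 13 subjects per group"; the Analysis section adds that "Statistical significance is inferred as a two-tailed P-value" below 0.05. An exact two-sample t calculation gives power 0.768 at 12 per group and 0.803 at 13, so 13 reproduces. At the planned 15, power is 0.860. This concerns T2* only. The documents give no SD for flow or oxygen consumption and no body-size data.

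**Assumptions.** There is no true disease effect. The total is proportional to BSA. The between-person CV of the raw total is 20%, 25% or 30%. Mean BSA differs systematically by 4%, 8% or 12%. For orientation, the one CV that can be formed from the plan is 4/23 = 17%, but that is for T2*.

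**False significance of the raw t-test.** With 15 per group, df = 28 and two-sided 5%, the noncentrality is shift / (CV × √(2/15)), where √(2/15) = 0.365. For an 8% shift at CV 25% this is 0.08 / (0.25 × 0.365) = 0.876. Rejection rates from the noncentral t:

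| CV of raw total | 4% shift | 8% shift | 12% shift |
|---|---|---|---|
| 20% | 8.3% | 18.5% | 35.5% |
| 25% | 7.1% | 13.5% | 24.6% |
| 30% | 6.4% | 10.9% | 18.5% |

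The range is about 6% to 36%, against a nominal 5%.

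**Chance imbalance.** With an assumed BSA SD of 0.2 m² around 1.9 m², the standard error of the difference in mean BSA is 0.2 × √(2/15) = 0.073 m², or 3.8%. That variation is already part of the raw CV, so the t-test allows for it. Simulation with equal size distributions (40,000 runs, raw CV 25%, size CV 10%) gives 5.0% rejection.

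**Dependence on proportionality.** Let the total scale as BSA to the power b. An 8% size shift then moves the raw mean by a factor of 1.08^b and the mean of total/BSA by 1.08^(b−1). With raw CV 25% and size CV 10%, simulated rejection rates with no disease effect are:

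| b | raw t-test | t-test on total/BSA |
|---|---|---|
| 1 | about 13% | about 5% |
| 0.5 | about 7% | about 7% |
| 0.25 | about 6% | about 9% to 10% |

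Dividing by BSA removes the problem at b = 1, changes nothing at b = 0.5, and makes matters worse at b = 0.25. A linear model of the total on group and BSA estimates the slope instead of fixing it; in the same settings it stays at about 5% for all three values of b.

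**Precision.** At b = 1, removing size reduces the CV from 25% to √(0.25² − 0.10²) = 22.9%. In the linear model a systematic size difference takes some of this back. An 8% shift against a size CV of 10% is 0.8 SD, so the variance of the group effect is inflated by about 1 + 0.8²/4 = 1.16 and its standard error by about 1.08. The effective CV is then 22.9% × 1.08 ≈ 24.7%, close to the original 25%. The reason for the change is bias, not power.

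**The case against.** The strongest reply is that the plan is silent rather than wrong. It gives no units and does not exclude indexing. That the two quantities are totals is inferred from how they are measured, and the Background calls the oxygen-consumption estimate hypothetical. This stands: a reader might infer a scaling error, but the documents support only that the scaling is unspecified and that the stated test, taken as written, makes no allowance for size.

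The second reply is that the inflated rates need a systematic size difference, and nothing in the documents shows one. This also stands. A reader might infer that small unmatched groups are enough to inflate the error through chance imbalance. They are not, as the simulation shows.

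Third, a reader might take the eGFR unit as a precedent and conclude that per-1.73 m² values should simply replace the raw ones, with a gain in effective sample size. The unit appears in an exclusion threshold for an estimate from creatinine, which is not an end-point, so there is no internal inconsistency. Any gain depends on near-proportional scaling, for which the documents give no evidence.

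Finally, the reach is narrow. Both end-points are exploratory, and the flow and consumption hypotheses concern change after SGLT2 inhibition. Size is also only one of several possible differences in a non-randomized comparison. All true; this limits the importance of the point. It does not justify leaving size out when weight and height are already collected.

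**Conclusion.** The point holds in a limited form. For two exploratory end-points, in the baseline patient-control comparison only, the stated analysis cannot separate a systematic body-size difference from a disease effect. Under the stated assumptions (proportional scaling, CV 20% to 30%, mean BSA difference 4% to 12%), false significance would be about 6% to 36% instead of 5%. Neither the direction nor the presence of a size difference can be established from the documents, and weaker scaling makes the effect smaller.

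A reader might extend this to the main results. The documents do not support that: the dapagliflozin-placebo contrast is within patient, so body size does not bias it, and T2*, the primary end-point, is not a total. Nor does the point affect the sample size. It is a low-cost improvement worth making before the data are analysed, partly because leaving the scaling open would permit a choice between raw and indexed values after the results are known.

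**What to change.** Add to the Analysis section, for the baseline patient-control comparison of renal artery flow and renal oxygen consumption only:

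- Compute BSA from the Visit 1 weight and height, naming the formula.
- Replace the unpaired t-test with a linear model of the end-point on group and BSA, and report the adjusted group difference with its confidence interval. This does not require exact proportionality.
- Report raw values and values per 1.73 m² alongside, as description.
- State the units of both end-points.
- Leave T2* and tissue perfusion unindexed, and leave the crossover analysis as it is.

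The cost is one degree of freedom (27 instead of 28 with 15 per group), a somewhat wider standard error when the groups do differ in size and the end-point follows size only weakly, and a little more analysis work. No new measurement, visit or participant is needed. The model deals with size only; other differences between unmatched groups remain, and the comparison should be described as observational.

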The sodium-glucose cotransporter-2 (SGLT2) is selectively expressed in the human kidney, where it executes reabsorption of filtered glucose with a high capacity. As a therapeutic target, SGLT2 has been successfully engaged by orally active, selective agents. SGLT2 inhibition (SGLT2i) has a range of known physiological effects: Glycosuria, natriuresis, plasma volume reduction, blood pressure reduction, increased lipid oxidation and ketogenesis (2). However, only few studies have described renal physiologic effects of SGLT2 inhibition in humans, where it has been observed that hyperfiltration and renal plasma flow is reduced during clamped euglycemia in type 1 diabetes (3).

SGLT2i have been observed to reduce cardiovascular mortality and to be associated with slower progression of diabetic kidney disease in the EMPA-REG-trial (4, 5); to reduce risk of cardiovascular events and kidney failure in the CREDENCE-trial (6); to slow progression of albuminuria in the CANVAS-trial (7); and to reduce the risk of renal events in the DECLARE-trial (8). The SGLT2 inhibitor dapagliflozin, used in the DECLARE study, reach peak plasma concentration after two hours and based on glucose excretion, the renal effects seem to be present after a few hours. The half-life is approximately 17 hours (9). The exact mechanisms of the beneficial effects of SGLT2 inhibition in diabetes is still unknown, but several hypotheses have been suggested. Hypoxia might play an important role.

Renal hypoxia

The kidneys have a high oxygen consumption, needed for reabsorption of filtered solutes, mainly sodium. While the renal cortex has a high perfusion, the renal medulla has a low

perfusion and at the same time a high oxygen demand needed for sodium reabsorption in the ascending loop of Henle, making it more prone to hypoxia. The presence of hypoxia has been demonstrated in diabetic kidney disease compared to age-matched healthy controls (10). At the same time, there is strong evidence of tissue hypoxia playing a central pathogenic role in the development of chronic diabetic kidney disease (11, 12). This is supported by a recent study showing that renal cortical hypoxia predicts decline in renal function in subjects with chronic kidney disease (13).

In diabetes, a number of factors can act together and increase the risk of renal hypoxia (14):

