SAEs, SARs, SUSARs will initially be reported to the sponsor within 24 hours. Previous non-serious AEs, which becomes SAEs follows the reporting of SAEs.

Sponsor must ensure that all information on SUSARs that are fatal or life-threatening is recorded and reported to the Danish Medicines Agency (on their web-based forms) as soon as possible and no later than 7 days after the sponsor became aware of such possible side effects. Within 8 days after reporting the sponsor must notify the Danish Medicines Agency all relevant information about the sponsor and investigator's response to the alert and consequence for the study conduct.

All other SUSARs will be reported to the Danish Medicines Agency within 15 calendar days after the sponsor became aware of them. Furthermore, the investigator should notify AstraZeneca when expediting SARs or SUSARs to health authorities and should report all SARs related to the product to the local AstraZeneca affiliate safety department. The submission to AstraZeneca must be within day 15 from the investigator's first knowledge about a valid case. Where required in national law the investigator should also expedite SARs or SUSARs, to Independent Ethics Committee (IEC)/Institutional Review Board (IRB).

All SUSARs will be unblinded before reporting to the authorities. All investigators have the authority to immediately unblind study medication if necessary.

Data on other AEs, including abnormal laboratory values as assessed by the investigator as clinically significant will be collected and recorded on standardized AE forms at each contact. These data are reported to relevant authorities in accordance with applicable laws and ICH-GCP guidelines.

When reporting SAEs and SARs the following parameters must be recorded: study name, patient identification (subject number, initials, sex, age), event (preferably a diagnosis), investigational medicinal product (IMP), reporter identification (name or initials), causality, outcome

Definition of adverse event

Any untoward medical occurrence in a patient or clinical investigation subject administered/using a product and which does not necessarily have to have a causal relationship with this treatment.

An adverse event can therefore be any unfavourable and unintended sign (including an abnormal laboratory finding), symptom, or disease temporally associated with the use of a product, whether or not considered related to the product.

Reporting of adverse event

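### Table 2 omits adverse-event collection at V1 and schedules none after V5, which falls about 12 hours after the last dose

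*Combined protocol and SAP*

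**What the plan says.** The reporting period is set under Reporting of adverse event: "This includes events from the first study-related activity after the subject has signed the informed consent", and the sentence goes on to run the period to the study's end. The same paragraph hands the timing to Table 2: "Timelines for reporting of AE's is described in study timetable". Under Reporting of SAE SAR and SUSAR, data on other (non-serious) events are to be "collected and recorded on standardized AE forms at each contact".

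The row in Table 2 reads "Adverse events x x x x", and the four marks stand under V2, V3, V4 and V5. The information visit and V1 have none. V1 is a contact after consent: the visit is headed "Visit 1 (day 7±6) at Steno Diabetes Center Copenhagen", while consent is obtained at day 0. V1 includes a 21 ml blood draw and follows 24 hours without medication other than long-acting insulin.

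For the end of collection, the Visit 3 section puts the second dose of a period at 21:00 on the evening before the visit, and V5 repeats V3. Assessment of efficacy gives the interval for the V3 and V5 measures: "baroreflex sensitivity are obtained before intervention (baseline) and 12 hours after intervention". No contact is listed after V5. The end of study is not defined for the individual participant. The Timeframe section equates study completion with the last participant's last visit.

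**The concern.** The text and the timetable disagree at the start of the reporting period, and the timetable stops very early at the end of it.

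At the start, staff who work from Table 2 would not ask about events at V1, although the text requires recording at every contact and counts events from consent.

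At the end, the last planned question about adverse events comes within one half-life of the final dose. Anything that appears later is found only if the participant volunteers it. For placebo-first patients that final dose is dapagliflozin 50 mg, which the protocol itself describes as larger than the usual daily dose. The end-of-study report on adverse events goes to the medicines agency, the ethics committee and the manufacturer, and it can contain only what was ascertained.

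**Working it through.** **Inputs.** Second dose at 21:00 before V3 and V5 (Visit 3; Visits 4 and 5). Interval from dose to measurement 12 hours (Assessment of efficacy). Half-life about 17 hours (Background, SGLT2 inhibitors). Nominal days: V1 7, V2 14, V3 28, V4 42, V5 66 (Table 2). Fifteen randomized patients, two sequences at 1:1.

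**The protocol's own interval.** From 21:00 to 09:00 is 12 hours, which agrees with the stated figure. The clock time of V3 and V5 is not given, so 09:00 is an assumption. A start between 08:00 and 10:00 gives 11 to 13 hours.

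**Drug remaining at the last contact**, assuming simple first-order decay:
- 12/17 = 0.71 half-lives, and 2^(−12/17) = 0.61, so about 61% remains.
- Five half-lives: 5 × 17 = 85 hours (about 3.5 days), and 2^(−5) = 0.03, so about 3% remains.
- From V5 to that point: 85 − 12 = 73 hours, about three days.

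**Scheduled follow-up after the second dose of each period:**
- Period 1: day 27 at 21:00 to the V4 dose on day 42 at 09:00 = 14.5 days.
- Period 2: 12 hours, to V5.

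**Who is affected.** At 1:1, 7 or 8 of 15 patients take dapagliflozin in period 2. There are 15 × 2 = 30 planned active doses, so 7 or 8 of 30 (23% to 27%) have the short follow-up. The other 7 or 8 patients take placebo in period 2, and their last placebo dose is cut off in the same way.

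**Does this unbalance drug and placebo?** From first dose to the end of the period, period 1 runs 28 days (day 14 to 42) and period 2 runs 24 days (day 42 to 66). With 8 drug-first and 7 placebo-first patients:
- Drug: 8 × 28 + 7 × 24 = 392 patient-days.
- Placebo: 8 × 24 + 7 × 28 = 388 patient-days, about 1% apart.

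Table 2 also places V5 at week 8, and Study duration gives eight weeks (day 56). Period 2 would then be 14 days:
- Drug: 8 × 28 + 7 × 14 = 322. Placebo: 8 × 14 + 7 × 28 = 308. These are about 4.5% apart.

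Counting only the time after the second dose:
- Drug: 8 × 14.5 + 7 × 0.5 = 119.5 patient-days. Placebo: 8 × 0.5 + 7 × 14.5 = 105.5.

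With 7 drug-first and 8 placebo-first patients, every pair is reversed. With equal sequences, every pair is equal. The inequality is therefore by period. Day 66 and week 8 need reconciling, but the 12-hour figure holds under either.

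**V1.** The gap from consent to the first mark in Table 2 is nominally 14 days, with V1 at day 7 inside it. No study drug has been given by then.

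**The case against.** A reader might infer from the short final window that adverse-event counts are tilted to make dapagliflozin look safer. The documents do not support that. The mirror-image sequence truncates the last placebo dose in the same way, and the totals above differ by 1% to 4.5% at an 8/7 split, in either direction. A real imbalance would need uneven sequences or differential dropout, and the protocol gives no reason to expect either. If the drug caused late events, losing them would understate the excess on drug, but the documents give no rate or onset time from which to size this. No comparison of adverse events by treatment is planned in the Analysis section either, so there is no planned contrast to repair.

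A reader might also infer that events before V2 go unrecorded. That is too strong. The text requires them, and they can be taken retrospectively at V2. The definition of an adverse event speaks of a subject given a product, which may explain a row that starts at V2, but the reporting section sets the start at consent. These events precede any dose and cannot affect a drug–placebo comparison.

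It can fairly be said, too, that V5 is only the last scheduled contact. Serious events must reach the sponsor within 24 hours whatever Table 2 shows, and investigators undertake to follow up complications. In placebo-first patients the first active dose, at V4, is followed for weeks. Setting 14.5 days against 12 hours as a ratio would exaggerate the matter, since on the protocol's half-life little drug remains after about 85 hours.

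All of this stands, and it limits the point. It does not supply a contact after V5: the 24-hour rule governs how fast a known event is passed on and does not plan for anyone to ask.

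**Conclusion.** The point holds as a gap in ascertainment. Table 2 conflicts with the text at V1. The last scheduled enquiry falls about 12 hours after the final dose, with about 61% of it remaining. In placebo-first patients, about a quarter of all planned active doses (7 or 8 of 30), events beyond that time have no scheduled capture. How many events would be missed cannot be derived from the documents.

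The figures rest on a V5 start near 09:00, first-order decay at the stated half-life, nominal visit days and sequences close to 1:1. The difference is between periods and falls about equally on drug and placebo. It does not threaten the primary endpoint. It is worth correcting because correction is cheap and safety after the final active dose is otherwise left to spontaneous report.

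**What to change.** 1. Mark adverse events at V1 in Table 2, so that it agrees with the reporting text.
2. Add one telephone contact for adverse events after V5, at least about 85 hours after the last dose (about three days after V5), for all randomized patients in both sequences. The investigators may choose a later time if they want to catch events of slower onset.
3. Define each participant's end of study as that contact, and align Study duration with it. Reconcile day 66 with week 8 for V5 at the same time.

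The cost is one mark in a table, a sentence of definition, about 15 short calls and a slightly later end of study for each patient. No additional analysis by treatment is needed.
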